5.6 Key exclusion criteria

- 1. Individuals who plan to move out of the study microcluster within 6 months
- 2. Individuals who are unable to fully consent and participate based on CC team assessment
- 3. Individuals who are not the primary caregivers of children ages 3-17 years

6. Subject recruitment

Participant recruitment will commence in September 2022 and will run through March 2024. Recruitment in control and intervention microclusters will occur simultaneously. The data analyst who performed the randomization will randomize microcluster order (stratified by intervention and control status and city section) to determine the order in which recruitment occurs.

Several Community Coordinator (CC) teams will be recruiting participants. A given team of two will remain in a microcluster until a total of 12 participants are fully enrolled in that microcluster. They will then move to the next microcluster on the randomly generated list. Multiple microclusters will be undergoing enrollment simultaneously. The CC team will be blinded to what arm of the trial the microcluster is in until all participants are enrolled. Participants will also be blinded until after everyone in that cluster is enrolled.

When starting recruitment in a new microcluster, the CC team will first place door knockers on all homes within the microcluster boundaries to alert neighbors to the presence of the study team in the neighborhood. They will then begin door-to-door recruitment at a pre-determined house that is closest to the geographic center of the study microcluster. They will follow a pre-determined route throughout the neighborhood that includes walking up one side of the street and back down the other side of the street before moving on to an adjacent block, and the next adjacent block, etc. The block order will be pre-determined by the data analyst performing randomization to where blocks will be ordered as closet to concentrically in a clockwise manner from the first block.

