Within the city section strata, we conducted a covariate-constrained randomization process in order to ensure balance between microclusters randomized to intervention and those randomized to control based on relevant sociodemographic variables. Covariate-constrained randomization quantifies baseline imbalance of microcluster-level covariates (both categorical and continuous) across all microclusters using a balance metric and then randomly selects one randomization schema from those with acceptable balance. Furthermore, the intraclass correlation coefficient calculation – a measure of reliability – remains unaffected under a constrained randomization model.²

We chose the following covariates to balance on: age (categorized by shares under age 19, 19-49, 50-64, and 65 and above); gender; median income; unemployment rate; amount of vacancy; and tree canopy. We did not balance on race/ethnicity (e.g., % Black) or poverty rates, since initial criteria for study site selection focused on census tracts whose populations were at least 80% Black and with elevated poverty rates. The covariates were measured based on their distribution of means by each microcluster using block group data from the US Census Bureau's 2020 ACS. Each microcluster's mean is the weighted mean for the covariates based on percent of land area in each census block group in which the microcluster sits. A microcluster could be in one census block group or could cross over 2 or 3 census block groups. Following the literature, we used a threshold of 0.2 for standardized mean differences in the covariates.

We used the -cvcrand- package, specifically the -cvrall- function, in R to calculate the final covariate balance metric and selection schema at random after covariate balance by cluster was achieved.²

Enrollment

Participant recruitment will commence in September 2023 and will run through May 2023 (or until we enroll at least 480, but no more than 720, in the main trial). Recruitment in control and intervention microclusters will occur simultaneously. The data analyst who performed the randomization will randomize microcluster order (stratified by intervention and control status and city section) to determine the order in which recruitment occurs.

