IGNITE Kids referrals. To support enrollment efforts for the IGNITE Kids sub study, participants may also be asked if they know of and are willing to connect the study team to any families in their neighborhood with children ages 3-17. Participants will be compensated \$10 for successful referrals. Referrals for IGNITE Kids will count towards the 2-referral limit described above.

Tree referrals. To support efforts in planting at least 10 trees in each intervention microcluster, participants will be invited to refer neighbors who may be willing to receive free trees through the study. Referrals may be accepted at the time of enrollment and/or during subsequent home visit(s). Participants will be compensated \$10 for successful referrals. Participants can make and be paid for an unlimited number of tree referrals or for the amount needed until tree planting goals have been met in their particular microluster.

Intervention

Place-Based Interventions

Our suite of place-based interventions consists of four separate interventions which will all be performed simultaneously in all of the intervention microclusters. The four interventions are: vacant lot greening, tree planting, weekly trash pickup, and abandoned house remediation. The first three will be performed through the Pennsylvania Horticultural Society (PHS), while the last will be performed through the City of Philadelphia.

After microclusters have been selected and randomized to the intervention arm (n=30), we will conduct an inventory of the locations of existing vacant lots, abandoned houses, and tree canopy. All place-based interventions will start in April 2023. See below for protocol for each intervention including the intervention timeframe for each.

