After connecting participants with the Clarifi team, participants will then be directly connected to BDT and CFW using a similar approach. BDT provides a screening tool that determines which benefits individuals are eligible for. The CC team will set up a time based on the participants' availability to complete this screening process with them in person. the participants have completed the screening process, they will call the phone line that BDT created for our study where a BDT representative will then walk the participants through the application process for benefits.

CFW provides both virtual and in-person (at several dedicated locations in the city) tax preparation services. Participation in these services will be confirmed in the same manner as the Clarifi services with the CC providing pre-selected appointment slots to the participants.

By the end of the intervention period in August 2024, the goal of the financial intervention will be for intervention group participants to have worked with a Clarifi counsellor at least 2 times and to have received a one time \$400 cash grant, completed the benefits screening, application and follow-up process with BDT one time, and filed income taxes with CFW.

At the end of the intervention period, participants in the control group will receive a list comprising of each of the financial partners and their contact information, but will not receive the further engagement and support to enroll in these services; nor will they receive the \$400 cash grant. Provision of information to this group goes one step beyond current outreach efforts by the financial partners, which include direct mailers and advertising.

9. Analysis plan

Outcome Measures

The primary and secondary outcomes for this study are described in detail **Table 1**. Primary outcomes will be drawn from our two-wave survey of study participants (one baseline wave and one endline wave); our secondary outcomes will be drawn from the same survey as well as from key administrative data sources (detailed in **Table 1**).

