For secondary outcomes based on microcluster-level administrative data, we will use a difference-in-differences strategy, which leverages additional power from repeat (quarterly) observations that are available in administrative data.¹⁶ Specifically, we will estimate a Poisson-fixed effects model for each secondary outcome on the interaction between binary indicators for calendar time (quarter-year) and binary indicator of intervention status, adjusting for cluster and calendar time (quarter-year) fixed effects (the cluster fixed effect subsumes the main effect for treatment status); microcluster populations at baseline will be used as the exposure terms. This approach is known as an event study specification.¹⁷ The time period of analysis will comprise the 8 quarters prior to intervention and all quarters over the course of the intervention period, which comprises the duration between the end of enrollment and baseline survey data collection to the beginning of follow-up data collection, and the post-intervention period, which all quarters between the beginning and end of follow-up survey data collection. (As data becomes available, we will, in the future, also conduct separate analysis that includes periods 8 quarters after the end of survey data collection, once these data become available. This analysis will be viewed as an extension of our primary difference-in-differences model to assess whether treatment effects were sustained after intervention period ended.)

The coefficients on the terms interacting treatment status with time periods prior to the intervention serve as visual and statistical checks of the parallel trends assumption, which we expect to hold given the randomized

selection of intervention and control groups. However, to address potential failures of the parallel trends assumption, we will conduct a specification test in which we will estimate and trend out of the post-intervention period any differential pre-intervention trends in outcomes between the two groups.¹⁷ The coefficients on the terms interacting treatment status with time periods after the intervention period will recover the overall (dynamic) intervention effect.

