Reasons for not spending time in greenspace	Things that stop an individual from spending time in greenspace (adapted from Evenson et al 2013 Environment and Behavior)	Survey	Categorical (weather (too cold or too hot), safety concerns, no time, too tired, I don't like spending time outside, other, nothing stops me from spending time outside in greenspace)	Baseline, 24 months

Perception of tree cover	Beliefs about number of trees in the neighborhood (internally developed)	Survey	Categorical (need more trees, enough trees, need less ttrees, unsure)	Baseline, 24 months
Tree planting concerns	Whether or not individual has concerns about planting more trees in neighborhood (internally developed)	Survey	Binary indicators for any concerns (=1)	Baseline, 24 months
Perceived tree health benefits	Whether or not individual believes trees confer health benefits (e.g., safety, mental health benefits, physical health benefits, social benefits, environmental benefits, aesthetic benefits)	Survey	Binary indicators denoting belief of any health benefits (=1) and separate indicators for each type of benefit	Baseline, 24 months
Stress and Agency				
Perceived stress	Perceived Stress Scale	Survey	Continuous (scale)	Baseline, 24 months
Neighborhood Perceptions				
Time spent in neighborhood	If individual endorses spending time relaxing, socializing, or hanging out in porches, stoops, and front yards of neighborhoods (adapted from Kahneman et al 2004 Science)	Survey	Continuous (scale)	Baseline, 24 months
Neighborhood social capital	Neighborhood Social Cohesion & Exchange and Social & Physical Disorder Scales	Survey	Continuous (scales)	Baseline, 24 months
Physical disorder	Whether or not participant reports a lot of abandoned buildings in their neighborhood (Ross and Mirowksi)	Survey	Binary (1 = yes)	Baseline, 24 months
Microcluster-Level Outcomes				
Neighborhood crime rates	Number of violent crimes, serious crimes	Philadelphia Police Dept. Crime Data - open access	Continuous (rate)	Quarterly data from 8 quarters prior to enrollment and 4 quarters after intervention period complete

Table 2. Child Health Outcome Measures

	Secondary Child Health Outcomes				
Outcome (by domain)	Measure	Data Source	Type of Data	Timeframe	
Health					

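### The pre-period for the microcluster difference-in-differences models is anchored on intervention in Section 9 but on enrolment in Tables 1 and 2, and with enrolment to March 2024 the Section 9 window would include about four treated quarters.

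*Combined protocol and SAP*

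**What the plan says.** Section 9, under microcluster level secondary outcomes, fixes the window: "The time period of analysis will comprise the 8 quarters prior to intervention", followed by the intervention and post-intervention quarters. It defines the intervention period as that "which comprises the duration between the end of enrollment and baseline survey data collection to the beginning of follow-up data collection". The post period is "the post-intervention period, which all quarters between the beginning and end of follow-up survey data collection".

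The Timeframe column for neighborhood crime (Table 1) and for preterm birth and low birth weight (Table 2) reads: "Quarterly data from 8 quarters prior to enrollment and 4 quarters after intervention period complete". The school and hospital-record rows of Table 2 use annual data starting 2 years before enrolment.

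The dates that would place these anchors disagree:

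- Section 6: "Participant recruitment will commence in September 2022 and will run through March 2024".
- Section 8.2, Enrollment: "Participant recruitment will commence in September 2023 and will run through May 2023", an end that precedes its start.
- Section 8.2, Place-Based Interventions: "All place-based interventions will start in April 2023".
- Section 8.2, financial interventions: participants in the intervention arm are contacted within one month of enrolment and the baseline survey, and the end point is "By the end of the intervention period in August 2024".

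**The concern.** The standard model in Section 9 has two interaction terms, one for the intervention period and one for the post period, and names the second as the effect of interest. Any other quarter in the data is reference. The definition of the pre-period therefore decides what the effect is measured against.

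Two things can go wrong. First, Section 9 dates the intervention period from the end of enrolment, not from the start of delivery. If delivery starts earlier, treated quarters count as baseline and pull the estimate toward zero. They could also look like a differential pre-trend, which the planned specification test would then remove from the post period. Second, even with no treated quarter in either window, anchoring on enrolment or on intervention gives a different reference mean. The plan does not say whether enrolment means its start or its end, or how quarters between the anchors are classified.

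**Working it through.** The plan gives no power, event rate or SE for these outcomes, so there is no stated figure to reproduce.

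**1. Treated quarters in the Section 9 pre-period.** Inputs: end of enrolment (Section 6 or Section 8.2) and start of place-based work, April 2023 (Section 8.2).

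- Enrolment to March 2024: the 8 preceding quarters run from April 2022 to March 2024. Those from April 2023 to March 2024 are treated, which is 4 of 8.
- Enrolment to May 2023: counting whole quarters back from the end of June 2023, only April to June 2023 is treated, at most 1 of 8.

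With a constant effect d (log rate ratio) in every treated quarter and a fraction f of the baseline treated, the expected estimate is approximately d − f·d = d(1 − f).

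- f = 4/8: 0.5d, roughly halved.
- f = 1/8: 0.875d, a loss of about 12%.

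Delivery is phased (Section 8.2 has trees planted in September and October 2023), so an effect that builds up would be attenuated less than this.

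**2. Distance between the anchors when both windows are untreated.** September 2022 to April 2023 is 7 months, so k = 2 or 3 quarters depending on how the September quarter is counted. If the tables mean the end of enrolment, and Section 9 dates intervention from that same point, k = 0.

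**3. Size of the shift.** Assumptions: equal-variance quarterly deviations in the arm difference; m = 3 post quarters (follow-up from September 2024 to March 2025 spans 2 to 3); correlation ranging from none to an AR(1) component with correlation 0.8 carrying 70% of the variance. With independent quarters of variance s²:

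- Variance of the estimate with an 8-quarter baseline: s²(1/8 + 1/m) = s²(0.125 + 0.333) = 0.458s².
- In-between quarters dropped (two 8-quarter windows k apart): variance of the difference 2k·s²/64. For k = 2, √(0.0625/0.458) = 0.37 SE. For k = 3, √(0.09375/0.458) = 0.45 SE.
- Continuous table span (8 + k quarters containing the Section 9 window): variance of the difference s²[1/8 − 1/(8 + k)]. For k = 2, √(0.025/0.458) = 0.23 SE. For k = 3, √(0.0341/0.458) = 0.27 SE.

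Range over the correlation structures, with m = 3:

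| Reading of the tables | k = 2 | k = 3 |
|---|---|---|
| Continuous span | 0.17–0.23 SE | 0.22–0.27 SE |
| In-between quarters dropped | 0.28–0.37 SE | 0.39–0.45 SE |
| Enrolment means its end | 0 | 0 |

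Each entry is one standard deviation of the difference between the two estimates. With the tables' own 4 post quarters, the first two rows become 0.17–0.30 and 0.29–0.50 across both values of k.

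**4. Precision of a pooled baseline.** Using all 8 + k untreated quarters, independent case: √(1/10 + 1/3) = 0.658 against √(1/8 + 1/3) = 0.677 for k = 2, and √(1/11 + 1/3) = 0.651 against 0.677 for k = 3. Over the correlation structures, the SE is about 2 to 5% smaller than with either 8-quarter window.

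**The case against.** The strongest reply is that the tables set no rival baseline. The Timeframe column describes the data to be obtained, and the annual rows describe a continuous span. Read that way, the quarterly span contains the Section 9 window, and Section 9 alone states the period of analysis. This largely stands. It makes the conflict an ambiguity rather than two specified analyses, and it is why the smaller figures are the likelier ones. It does not say which of the collected quarters form the reference.

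The second reply is that enrolment to March 2024 is out of line with the rest of the protocol. Section 5.2 gives baseline collection 9 months. Sections 7 and 8.2 place follow-up about 24 months after enrolment, between September 2024 and March 2025, which implies enrolment from September 2022 to March 2023. Section 8.2 ends recruitment in May 2023. This also stands: the halved effect follows from one stated date that the others contradict. The March 2024 date is nevertheless in the current text.

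A reader might go further and infer that the two anchors are about 6 quarters apart (September 2022 to March 2024), so that the estimates would differ by about 0.65 SE by chance. The documents do not support this. The gap needs the March 2024 date and the assumption that in-between quarters are discarded, which no section states. On those dates the difference would also be bias, because four delivery quarters sit in the baseline.

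**Conclusion.** The mismatch is real and the passages must be reconciled. The more serious consequence is conditional: if enrolment ends in March 2024 and the effect is constant from April 2023, the Section 9 pre-period is about half treated and the estimate is roughly halved. With enrolment ending in May 2023, at most about one quarter in eight is affected.

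If neither window holds treated quarters, the choice is worth about 0.2 to 0.3 SE for a continuous span, about 0.3 to 0.45 SE if in-between quarters are dropped, and 0 if enrolment means its end. These figures need a 2 to 3 quarter gap, 3 post quarters and an assumed correlation structure; they are typical differences, not bounds.

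Two further inferences should be resisted. The SE figures do not carry over to the event-study coefficients, which are relative to a reference quarter that the plan does not name. Nor can every quarter before April 2023 be taken as untreated, since financial contact can follow enrolment within a month. All the outcomes concerned are secondary, so this is a worthwhile clarification rather than a threat to the trial's main conclusions.

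**What to change.** In Section 9 and in the crime, preterm-birth and low-birth-weight rows of Tables 1 and 2, state one baseline: all full quarters from 8 quarters before the start of enrolment to the last full quarter before any intervention delivery, place-based or financial, starts anywhere in the trial. Date the intervention period in these models from that start of delivery instead of from the end of enrolment. Apply the matching rule to the annual rows: from 2 years before the start of enrolment to the last full year before delivery starts. Reconcile the recruitment dates in Sections 6 and 8.2 so that the window can be placed on the calendar.

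The cost is wording, plus possibly a few more quarters of administrative data. The baseline may be slightly longer than 8 quarters. If delivery starts 2 to 3 quarters after enrolment opens, the SE is about 2 to 5% smaller. If financial delivery follows enrolment almost at once, the baseline stays close to 8 quarters and the gain in precision largely disappears, but treated quarters are still kept out.

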In addition to this "event study specification," we will also estimate a standard difference-in-differences model in which the calendar time $\times \times$ treatment interactions are replaced by intervention period $\times \times$ treatment interaction and a post-intervention period $\times \times$ treatment interaction. These two terms will capture average intervention impacts during intervention implementation and immediately thereafter, with the latter being the treatment effect of interest.

For all models, we will adjust standard errors for clustering at the study microcluster level. We will report both unadjusted and multiple-comparisons adjusted¹⁸ p-values for all outcomes.

Sub-group analyses

For our primary outcomes and survey-derived secondary outcomes, we will estimate the above GEE models separately for the following subgroups:

- Gender (persons identifying as men vs. persons identifying as women; if the sample size permits, we will also consider separate models for trans- and non-binary individuals)
- Level of education (split by the sample median years of schooling)
- Age (over 50 versus under 50)

We will assess statistical differences in treatment effects between categories within each subgroup by estimating versions of our main GEE models that fully interact all terms with the binary subgroup indicator, and assessing the standard error and 95% CI on the interaction between treatment and the subgroup indicator.

Evaluating Mechanisms

In addition to evaluating treatment effects on secondary outcomes, we will assess potential mechanisms underlying intervention effects on the primary outcomes using three *descriptive* (and exploratory) approaches.

First, we will use our survey data to examine the extent to which the non-health secondary outcomes (e.g., food security, financial security, social cohesion, stress, experiences of racism, exposure to crime, engagement with greenspaces, health care utilization) mediate the relationship between the intervention and any impacts on the primary outcomes. Specifically, we will conduct a causal mediation analysis to decompose intervention effects by each set of potential mediators. Our method will follow the strategy of Heckman et al (2013), who use an ordinary least squares based approach.¹⁹

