School performance	Grade point average	Philadelphia School District Data	Continuous	Annual data from 2 years prior to enrollment through 1 year after intervention period complete
Preterm birth	Rate of preterm birth (birth < 37 weeks gestational age)	Pennsylvania birth certificate data	Continuous (rate)	Quarterly data from 8 quarters prior to enrollment and 4 quarters after intervention period complete
Low birth weight	Rate of low birthweight (birthweight < 2000 grams)	Pennsylvania birth certificate data	Continuous (rate)	Quarterly data from 8 quarters prior to enrollment and 4 quarters after intervention period complete
Emergency room utilization	Emergency room visits in the previous 12 months	Children's Hospital of Philadelphia Electronic Health Record	Continuous (rate)	Annual data from 2 years prior to enrollment through 1 year after intervention period complete
Hospitalization	Number of hospitalizations in the previous 12 months	Children's Hospital of Philadelphia Electronic Health Record	Continuous (rate)	Annual data from 2 years prior to enrollment through 1 year after intervention period complete

Qualitative Analysis

We will use an applied thematic analytic approach to qualitative data analysis. Data analysis will coincide with data collection, enabling us to adjust data collection procedures to capture emerging and unexpected phenomena. Starting with the first 3-5 interviews, qualitative data will be coded in cycles by the coding team, led by [name] and performed by the Penn Mixed Methods Research Laboratory. The first cycle of coding will enable generation of a codebook grounded in the data (de novo codes) and in a priori codes reflecting

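### Preterm birth and low birth weight are assigned to periods by calendar quarter with no allowance for gestation, so the intervention and post-intervention terms do not measure what their labels say

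*Combined protocol and SAP*

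**What the plan says.** Section 9 (Microcluster level secondary outcomes) sets one approach for every outcome taken from administrative data: a Poisson fixed-effects model with treatment interacted with calendar quarter, followed by a pooled model with two period terms. Of the pooled terms it says: "These two terms will capture average intervention impacts during intervention implementation and immediately thereafter, with the latter being the treatment effect of interest".

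The periods follow survey milestones. The intervention period is the one "which comprises the duration between the end of enrollment and baseline survey data collection to the beginning of follow-up data collection". It is followed by "the post-intervention period, which all quarters between the beginning and end of follow-up survey data collection". Table 2 lists preterm birth and low birth weight, from birth certificates, as microcluster-level rates with this timeframe: "Quarterly data from 8 quarters prior to enrollment and 4 quarters after intervention period complete".

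The dates are in Section 8.2. "All place-based interventions will start in April 2023", and the financial component refers to its goals "By the end of the intervention period in August 2024". Follow-up surveys run from September 2024 to March 2025 (Subject compensation; Section 8.2, Enrollment).

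No section gives a lag, a conception-date rule or a measure of exposure during pregnancy for births. Assignment by quarter of birth is not spelled out, but it is the natural reading of a quarterly rate from birth certificates.

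**The concern.** The coding suits an outcome such as crime, where a quarter's count reflects that quarter's conditions. A birth outcome forms over the whole pregnancy. A birth early in the intervention period comes mostly from a pregnancy that predates the work. A birth just after August 2024 comes from a pregnancy spent almost entirely under it.

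Two things follow. The intervention-period term mixes pregnancies with little, partial and full exposure, so any effect of exposure during pregnancy is diluted. The post-intervention term, which the plan names as the effect of interest, largely reflects pregnancies that began during the intervention. Its description as an effect arising immediately afterward does not fit these two outcomes.

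**Working it through.** The plan gives no figure for this point, so there is none to reproduce. The check is date arithmetic.

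**Inputs from the plan.** Intervention April 2023 to August 2024, which is 17 months. (Section 5.2 says 18 months.) Follow-up September 2024 to March 2025, which is 7 months. Table 2 window: four quarters after the intervention.

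**Assumptions.** Nine-month gestation, births spread evenly over time, and exposure counted in full from April 2023.

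**Formula.** Set month 0 = start of April 2023 and month 17 = end of August 2024. For a birth at month b, the exposed share of gestation is the overlap of (b − 9, b) with (0, 17), divided by 9.

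**Post-intervention births**
- September 2024 to March 2025 (b from 17 to 24): share = (26 − b)/9. The mean is [(9² − 2²)/18]/7 = 4.278/7 = 61%. Conception falls in months 8 to 15, all inside the intervention.
- Table 2 window (b from 17 to 29): mean = 4.5/12 = 38%. Conceived before the end of August 2024: 9/12 = 75%.
- By exact dates at 40 weeks (266 days from conception), births in the follow-up window were conceived between 10 December 2023 and 8 July 2024. Mean exposed gestation is 60%: 95% for September 2024, 72% for the fourth quarter of 2024 and 37% for the first quarter of 2025.
- Exception: 31 August 2024 to 31 March 2025 is 212 days, and 212/7 + 2 = 32.3 gestational weeks. Births at about 32 weeks or less, late in the window, can have been conceived after August 2024. If 1% to 4% of births are that early, averaging 28 weeks (assumption), 14.2% of them qualify, which is about 0.1% to 0.6% of births in the window. All of these are preterm events.

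**Intervention-period births.** The answer depends on when the coded period starts. Section 9 ties that to the end of enrollment, which the plan dates in three ways.

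| End of enrollment | Coded period | Conceived before April 2023 | Conceived before coded period | Mean exposed gestation |
|---|---|---|---|---|
| March 2023, implied by 24-month follow-up | April 2023 to August 2024 | 266/519 days = 51% | 51% | (4.5 + 8)/17 = 74% |
| May 2023, Section 8.2 (stated start is later than the end) | June 2023 to August 2024 | 205/458 = 45% | 266/458 = 58% | (4.278 + 8)/15 = 82% |
| March 2024, Section 6 | April to August 2024 | 0% | 153/153 = 100% | 100% |

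The two conception columns use 40-week births; the last column uses the nine-month formula. On the nine-month rule the 51% becomes 9/17 = 53%, and with an 18-month period it is 266/549 = 48%. If the effect is proportional to exposed gestation, the dilution is 26%, 18% and 0% in the three rows.

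The March 2024 date also disturbs the post period. Surveys 24 months after enrollment would then run to March 2026, and 311/577 = 54% of 40-week births from September 2024 onward would be conceived after the intervention ended.

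**Sensitivity to rollout.** Section 8.2 has lots greened April to June 2023, houses remediated April to August 2023 and trees planted September to October 2023. Counting exposure only once all of these are in place (month 7), mean exposed gestation for an April 2023 period is 5.5/17 = 32%, while the follow-up window stays at 61%.

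**The case against.** Several objections stand.

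- Births in a given quarter are compared between randomized arms, so both terms are valid contrasts. A reader might infer bias or an invalid test; the documents do not support that.
- A reader might infer that an effect ending in August 2024 would be reported as sustained. The plan reserves that question for a separate extension covering 8 quarters after survey collection ends. On the same arithmetic, births in 22 of those 24 months (92%) are conceived after the intervention.
- Dilution falls on the intervention-period term, which is not the effect of interest. Calling those births mostly unexposed would also overstate it: the mean is 74% on an April 2023 start, and only the first quarter (17%) is mostly unexposed.
- The quarter-by-quarter event study comes first in the plan, and a gestational ramp should be visible in it.
- Greened lots and trees may keep acting after August 2024, so gestation beyond that date is not necessarily unexposed.
- The plan does not say that record-level birth data will be supplied, or that residence at conception is known.

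These points limit the consequence but do not remove the mismatch. The pooled post term is still the declared effect of interest, and its description does not fit births. The event study shows timing by quarter of birth but supplies no estimate for a defined exposure in pregnancy.

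**Conclusion.** The point holds as one of dilution and labelling for two secondary outcomes; the primary analysis is untouched. On the stated intervention and follow-up dates, the post term for births is essentially an estimate for pregnancies begun during the intervention. If the effect were proportional to exposed gestation and ended in August 2024, that term would still show about 61% of the full effect, or 38% over Table 2's window. Both conditions are assumptions.

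Two stronger statements go too far. It is not exact that every post-intervention birth was conceived during the intervention, because a few very preterm births late in the window may not have been. Nor is about half a fixed share of intervention-period births: it needs a period starting around April 2023, and the enrollment dates leave that open. Under the March 2024 date, none were conceived before April 2023, but all were conceived before the coded period opens. Even there, conception and period do not line up. Those dates, and the differing outcome windows in Section 9 and Table 2, must be reconciled before any single figure is quoted.

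**What to change.** For preterm birth and low birth weight only:

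1. Estimate conception from birth date and gestational age, with the dating convention stated. Form cohorts according to whether a fixed 37-week window from conception lies wholly before, partly after or wholly after the intervention start. Estimate the treatment interaction for each cohort. The fixed window prevents a short gestation from lowering its own exposure.
2. Include only conception cohorts whose births would all fall inside the data window; a truncated cohort would be selected on gestation length.
3. Keep the quarter-of-birth event study as a descriptive figure, and state that the calendar post term is not read as a post-intervention effect for births.
4. Use the share of the 37-week window inside the intervention dates only as a sensitivity analysis, since it assumes that exposure ends in August 2024.
5. Reconcile the end of enrollment, the period definitions and the outcome windows across Sections 6, 8.2 and 9 and Table 2.

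The cost is modest: analysis-plan wording, plus birth date and gestational age extracted per record. Gestational age is already needed for the preterm definition, and births must in any case be placed in microclusters. The latest conception cohorts drop out until the later data anticipated in Section 9 arrive. Moves during pregnancy remain a limitation if only residence at birth is available.
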